APPENDIX 1:

1. Informed Consent form for the patient - Versie 1.2
2. Informed Consent form for the legal representative of the patient - Versie 1.2
3. Opting out form for the patient - Versie 1.2
4. Informed Consent form for the healthy volunteer - Versie 1.2

1. Study Synopsis

Title of clinical study	The Dynamics of the ACTH and cortisol response to CRH stimulation during critical illness: A Randomized, double-blind, placebo-controlled crossover study
Protocol Short Title/Acronym	DACAR
Sponsor name	UZ Leuven
Principal Investigator	[name]. [name]
Medical condition or disease under investigation	Critically ill patients
Purpose of clinical study	To elucidate the central cause of the low circulating ACTH concentrations in the face of elevated circulating cortisol during acute, intermediate and prolonged critical illness
Primary objective	To document the ACTH and cortisol responses to exogenous CRH in patients with acute and prolonged critical illness
Secondary objective(s)	To describe the clinical causes/consequences of these changes
Study Design	Randomized, double-blind, placebo-controlled crossover study
Primary endpoints	The responses of plasma ACTH and cortisol to CRH and the changes hereof over time in ICU in relation to patient characteristics and outcome parameters
Sample Size	At least 120 patients - patient recruitment will continue until preset sample numbers are reached in 3 time-in-ICU-cohorts (40 patients per cohort) with a comparable distribution of ICU admission categories – and 20 healthy volunteers (controls who never stayed in the ICU)
Summary of eligibility criteria	Critically ill patients in the acute phase (ICU day 3-6), the intermediate phase (ICU day 7-16) and prolonged phase (ICU day 17-28) of critical illness
Maximum duration of treatment of a Subject	Not applicable
Version and date of final protocol	1.3; 05-07-2016
Version and date of protocol amendments	-

2. Background and rationale

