4.1 Patients

We will study unique patients from different time cohorts, with an increasing duration of critical illness, in order to have 3 sets of patients who represent 3 different time points in the course of critical illness:

Cohort 1: acute phase of critical illness: ICU day 3 to 6.

Cohort 2: intermediate phase of critical illness: ICU day 7 to 16.

Cohort 3: prolonged phase of critical illness: ICU day 17 to 28.

If a patient, who was included in an earlier cohort, is still in ICU at the time point of the next cohort recruitment, and still meets the inclusion criteria, the patient will be studied again according to the same study protocol. The results from these analyses within patients over time will not be included in the primary study to avoid bias due to multiple comparisons, but will be analyzed separately. The availability of such sequential responses over time within one patient will allow an additional longitudinal analysis of HPA-axis alterations during the time course of the disease.

Two times each week, all adult (age ≥ 18 y) patients from the population present in 5 ICUs from 2 departments (medical and surgical) in the University Hospital of Leuven will be screened for eligibility in the study. Patients will be included when written informed consent by the patient or patients' next of kin is given.

Inclusion criteria

All adult (age ≥ 18 y) patients at the surgical or medical intensive care units, with ongoing intensive care dependency, a stable condition for at least 48h, and an expected stay in ICU for at least 48h, are eligible.

Exclusion criteria

- Predisposing factors of adrenal insufficiency
 - Cerebral disease with intracranial hypertension threatening the neuroendocrine system
 - Pituitary disorders including (pan)hypopituitarism
 - Known adrenal disease (Cushing's syndrome or Addison's disease)
 - Chronic treatment with glucocorticoids, other steroids or anti-steroid chemotherapy within the last 3 months
 - IV administration of glucocorticoids within the last 72 hours
 - Use of etomidate within the last 72 hours
 - Use of azoles within the last 7 days

- Other drugs predisposing to adrenal insufficiency: phenytoin, rifampicin, glitazones, imipramin, phenothiazine, phenobarbital
- Patients known to be pregnant or nursing
- No arterial line or central venous catheter in place
- Ethical restrictions
 - Moribund
 - Declined participation

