Patient characteristics and outcome parameters: demographics (age, gender, BMI), medical history (diabetes, malignancy, renal replacement therapy), admission characteristics (reason for ICU admission, APACHE II score, SIRS and sepsis on admission), patient characteristics during ICU stay (clinical evidence of adrenal failure, SIRS and sepsis), ICU and hospital stay, ICU and hospital mortality.

Clinical parameters: Among others vital parameters (mean, systolic and diastolic blood pressure, pulse, temperature), mechanical ventilation, mean daily glycemia and renal function (daily urinary volume, creatinine clearance), infection.

Treatment information: all relevant treatments such as vasopressors and inotropes, treatment with opioids, anti-coagulants, insulin, and types and amounts of nutrients.

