5.2 Control group

Time profiles of ACTH and cortisol response to exogenous CRH are not clearly defined in the literature. Especially data from healthy volunteers with a comparable age, gender and BMI as our patient population are lacking. To compare the evolution of the ACTH and cortisol response during critical illness with healthy reference values, we will use the same study protocol as for the patients in 20 demographically matched healthy volunteers, with repetitive blood sampling during 2 consecutive mornings from 10.45-13.00 h, after receiving an alternate injection of CRH or placebo each morning. Volunteers will be asked to limit their morning nutritional intake to a European breakfast.

6. Compensation for control group

Healthy control subjects will be compensated for all expenses made to participate in the study, such as transportation cost and costs for parking space, and will be offered a meal on each study day and an overnight stay in Leuven. Furthermore, a gift card (value card worth 50 EUR) will be offered as an additional reward.

7. Statistics

First, the response to CRH injection (changes over time in plasma ACTH and cortisol concentrations) will be corrected for its corresponding placebo test result (changes over time in plasma ACTH and cortisol concentrations), resulting in a delta AUC value. The delta AUC values will be compared between each of the 3 cohorts and the healthy reference group, with correction for multiple comparisons with use of ANOVA (Bonferroni correction of the alpha error to correct for the multiple comparisons of each of the 3 patient cohorts with the healthy controls), after transforming the data to normally distributed values if needed. If the latter is not possible, non-parametrical tests will be used.

Second, for those patients from whom multiple CRH test results were collected, changes in delta AUC values within these patients will be analyzed with use of mixed models / repeated measures ANOVA after transforming the data to normally distributed values if needed.

Third, correlations between the ACTH and cortisol responses to exogenous CRH and clinical risk and outcome parameters will be done with the use of Pearson tests. Fourth, these measurements will be compared in patients with a favorable and a non-favorable clinical outcome.

8. Ethics and regulatory approvals

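### Correlations of the CRH response with length of stay should be adjusted for cohort, because each cohort sets a minimum stay

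*Protocol*

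**What the plan says.** Section 7 (Statistics) lists four steps. The first compares delta AUC between each patient cohort and the healthy controls. The second analyses repeated tests within patients. The third is the one at issue: "correlations between the ACTH and cortisol responses to exogenous CRH and clinical risk and outcome parameters will be done with the use of Pearson tests". The fourth compares patients with favorable and non-favorable outcomes. Cohort is not mentioned in the third or fourth step, and the text does not say whether patients are pooled.

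Section 5.1 lists among the stored outcome data "ICU and hospital stay, ICU and hospital mortality". The synopsis words the primary endpoint as the responses and their change over time in ICU "in relation to patient characteristics and outcome parameters". Section 3.1 makes the comparison across increasing duration of illness the primary objective, and possible causes and consequences the secondary one.

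Section 4.1 defines the three groups by the day of testing: days 3–6 for the acute group, days 7–16 for the intermediate group, and for the last group "Cohort 3: prolonged phase of critical illness: ICU day 17 to 28". Eligibility also requires "an expected stay in ICU for at least 48h".

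**The concern.** A patient tested on ICU day 17 or later has, by definition, an ICU stay of at least 17 days; a patient in cohort 1 need only have reached day 3. Hospital stay inherits the same minimum. Cohort therefore drives stay through the design, and the primary objective asks whether cohort also drives the response. If it does, a correlation over all 120 patients picks up the cohort effect a second time and presents it as a link between response and stay.

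The stake is interpretation. A reader would take the correlation as evidence that a weaker pituitary response foretells a longer stay, when it may only restate that patients tested later were tested later. Because the synopsis places the relation to outcome inside the primary endpoint, such a result could be reported prominently.

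A second problem concerns the same variable. Death ends a stay early, so a short stay can mean early recovery or early death. Section 7 does not say how deaths are handled in this step.

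**Working it through.** The protocol gives no figure for the correlation step, so there is none to reproduce. The check asks how often a pooled Pearson test is significant at two-sided 5% when response and stay are unrelated within every cohort.

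**Inputs from the protocol**
- 40 patients per cohort, 120 in total (section 4.3b).
- Mean delta AUC ACTH 2159 and SD 1136 pmol/L min, with a planned 30% reduction between two patient cohorts (section 4.3b). Shift: 0.30 × 2159 / 1136 = 647.7 / 1136 = 0.57 SD.
- Test-day windows 3–6, 7–16 and 17–28 (section 4.1).

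**Assumptions (not in the documents)**
- Test day is uniform within each window.
- ICU stay = test day + 2 days + an exponential remainder with mean 5, 10 or 20 days.
- The response falls by 0%, 15% and 30% over cohorts 1, 2 and 3 and is constant within a cohort.

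**Step 1: response and cohort.** Cohort means are 2159, 1835 and 1511. Between-cohort variance = (323.85)² × 2/3 = 69,919. Within-cohort variance = 1136² = 1,290,496. The size of the correlation of response with cohort (scored −1, 0, 1) is √(69,919 / 1,360,415) = 0.227, with negative sign.

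**Step 2: stay and cohort.** Mean test days are 4.5, 11.5 and 22.5, so the between-cohort variance is 54.9. The average within-window variance is (1.25 + 8.25 + 11.92)/3 = 7.1. With mean remainder 10 (variance 100), total variance is 162.0. Covariance with cohort score = (22.5 − 4.5)/3 = 6. Correlation = 6 / √(2/3 × 162.0) = 0.58. For mean remainders of 5 and 20 days it is 0.79 and 0.34.

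**Step 3: induced correlation.** With no link inside a cohort and a linear fall in response, r is the product of the two: −0.227 × 0.58 = −0.13.

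**Step 4: false-positive rate.** By Fisher's z, atanh(0.131) × √117 = 1.42, and P(|Z| > 1.96) is about 30%. For 5 and 20 days the same calculation gives 50% and 13%.

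**Simulation of trials with 3 × 40 patients**

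| Cohort pattern of response | Assumed mean remainder | Pooled Pearson significant | With cohort term |
|---|---|---|---|
| 0 / −15 / −30% | 5 days | 51% | 5% |
| 0 / −15 / −30% | 10 days | 30% | 5% |
| 0 / −15 / −30% | 20 days | 14% | 5% |
| 0 / 0 / −30% | 10 days | 33% | 5% |
| 0 / 0 / −15% | 10 days | 12% | 5% |
| no difference | 10 days | 5% | 5% |

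Repeat runs of the graded 30% pattern gave 30–31% at 10 days and 13–14% at 20 days, which agrees with the hand calculation.

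**Ranks do not help.** In a further simulation in which death could also end the stay, the graded 30% pattern gave 43% significant results with Spearman and 40% with Pearson.

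**Death.** Suppose cohorts do not differ and the response affects only the hazard of death (assumed hazard ratio about 0.5 per SD, mortality about 27%). Response and total stay then correlate at r about +0.12, significant in 23% of trials, although time to live discharge is unrelated to the response.

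**The case against.** **Pooling is not stated.** Section 7 names a test and leaves open whether it is run per cohort; adjustment might be set out in an analysis plan that is not at hand. This stands as a limit on the point: the inflation needs both pooling and a real cohort difference. But the protocol does fix a method for this step, and applied as written to all patients it carries the problem.

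**The tie is a minimum, not a fixed stay.** Section 4.1 foresees long stays among early entrants ("If a patient, who was included in an earlier cohort, is still in ICU at the time point of the next cohort recruitment"). That is correct, and it is why the cohort–stay correlation is well below 1 and the result depends on the assumed remaining stay.

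**Stronger readings do not hold.** A reader might infer that the Pearson tests are invalid, or that false links are bound to appear. They are not: in the planning scenario with a 10-day mean remainder, about 70% of trials would show no significant link. A reader might also object that mortality is binary. Pearson's test against a 0/1 variable gives the same p value as a two-sample t test (0.7040 both ways in a check), and mortality has no minimum set by cohort; with assumed mortality of 15/20/30% or 10/20/30% over the cohorts the error rate is only 7.0% or 8.5%. Nor does skew alone create false links: with a log-normal response and skewed stay the rate was 4.9%.

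**Reach is limited.** Variables fixed at admission, such as age or APACHE II, have no such minimum. For the favorable/non-favorable step, Section 7 does not define favorable; if it means survival, any distortion is likely to be the small one just given.

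**Conclusion.** The concern holds for length of stay, conditionally. If patients are pooled and the response differs between cohorts by the planned 30%, an unadjusted response–stay correlation is falsely significant in about 30% of trials (13–51% over the assumed range of remaining stay). A cohort term brings this back to about 5%, and without a cohort difference there is no inflation. The figures rest on the assumed distribution of remaining stay and on a response that is constant within each cohort. They were computed for ICU stay; hospital stay shares the minimum but was not simulated. The handling of death is a separate weakness of total stay as an outcome, and the 23% given for it rests on an assumed hazard ratio. The primary comparison of each cohort with controls is not affected.

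**What to change.** State in Section 7 that associations of the ACTH and cortisol responses with clinical and outcome parameters, including the favorable/non-favorable comparison, are adjusted for or stratified by cohort: for example a partial correlation, or a regression with a cohort term. Replacing Pearson with Spearman without a cohort term would not be enough.

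For stay, analyse time from the test day instead of total stay, with death taken into account, for example time to live discharge with death as a competing event, stratified by cohort. Counting from the test day removes the built-in minimum, including the spread of test days inside the wider windows.

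Logistic regression for mortality, and adjustment for APACHE II, are reasonable preferences but not needed to cure this problem.

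The cost is a change of wording, a little more analysis work and two degrees of freedom. Stay and mortality are already among the stored data and the test day is known by design, so no new data are needed.

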5.1 Patients group

After informed consent, each patient from each cohort will be randomized for the order of CRH or placebo injection into two crossover study groups. Consecutive patients will be randomly assigned to 'first placebo' or 'first CRH' using blinded envelopes, stratified according to the 3 'time in ICU' cohorts. At 11.00 am, after 2 baseline blood samples (EDTA, 4ml) (-15 and 0 min), 100µg CRH or placebo (0.9% NaCl) will be injected as an intravenous bolus. Blood samples (EDTA, 4ml) will then be obtained at 5, 10, 15, 30, 45, 60, 90, and 120 minutes after injection to determine plasma ACTH and cortisol concentrations. The next day, each patient will receive the alternate injection, and the same blood sampling protocol as the day before (Figure 1). Since for each participant the measured effect is the difference between the response to the injection of CRH and placebo, variability is reduced.¹⁶

Injections of CRH or placebo will be given through a peripheral or central venous catheter, followed by a flush with ±5 ml (depending on the distance between the injection point and the insertion point of the catheter) of normal saline (NaCl 0.9%) to guarantee a full injection of the entire dose, and blood samples are drawn from an arterial or central venous catheter, all in situ and inserted for clinical purposes. The total amount of blood sampled per session is 40ml (Good Clinical Practice (GCP) consists of 40 ml per day). Some patients may experience mild, brief facial flushing immediately after injection, but at this dose level no other side effects have been reported.¹⁸ Allergic reactions have also not been reported.

[figure not shown]

Figure 1: Study protocol. Patients from the 3 cohorts will be randomized for the order of CRH or placebo injection into two crossover subgroups. Each patients from each subgroup will be studied during a total period of 4.5 hours, with repetitive blood sampling during 2 consecutive mornings from 10.45-13.00 a.m.

The ACTH and cortisol responses to CRH/placebo will be correlated with available demographic and clinical data.

Such stored patient data include:

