The study will be conducted in compliance with the principles of the Declaration of Helsinki (2008), the principles of GCP and in accordance with all applicable regulatory requirements. This protocol and related documents is will be submitted for review to Ethics Committee.

The study can and will be conducted only on the basis of prior informed consent by the subjects, or their legal representatives, to participate in the study. We will obtain a signed informed consent form (ICF) for all patients prior to their enrollment and participation in the study in compliance with all applicable laws, regulations and the approval of the Ethics Committee. We will retain such ICFs in accordance with the requirements of all applicable regulatory agencies and laws.

The investigators shall treat all information and data relating to the study disclosed to the Investigators in this study as confidential and shall not disclose such information to any third parties or use such information for any purpose other than the performance of the study. The collection, processing and disclosure of personal data, such as patient health and medical information is subject to compliance with applicable personal data protection and the processing of personal data (Directive 95/46/EC and Belgian law of December 8, 1992 on the Protection of the Privacy in relation to the Processing of Personal Data).

Total blood loss per patient will be limited to 80 ml (GCP is 40 ml per day). Samples will be taken via the arterial line or central venous catheter, already in place as part of the standard of care for ICU monitoring, and thus no additional discomfort will be caused.

All laboratory measurements specifically required for this study will be performed in the Laboratory of Intensive Care Medicine and will thus not generate any cost for the patients or healthy control subjects.

9. Data Management

For reasons of data integrity and internal control during data input, the patient name will be stored in a separate table linked to the eCRF (electronic Case Report Form). However, these data will only be accessible for the authorized local research staff and the principal database manager on an individual login/password base. When the database is finalized, the identity data will be detached from the eCRF and stored at the local site. Data transferred within the research group will always be anonymous and limited to the data needed to address the question of the researcher.

10. References

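### The 80 ml limit on total blood loss per patient covers exactly one two-day test, so it cannot hold for patients whom section 4.1 has tested again (160 or 240 ml)

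*Protocol*

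**What the plan says.** Four places in the protocol bear on this.

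- **Section 8 (Ethics and regulatory approvals)** sets the limit: "Total blood loss per patient will be limited to 80 ml (GCP is 40 ml per day"). It does not tie the figure to one test or one cohort.
- **Section 5.1 (Patients group)** fixes the sampling. Each session begins "after 2 baseline blood samples (EDTA, 4ml) (-15 and 0 min"), and then "Blood samples (EDTA, 4ml) will then be obtained at 5, 10, 15, 30, 45, 60, 90, and 120 minutes after injection". The section gives the sum itself: "The total amount of blood sampled per session is 40ml". The crossover is completed on the following morning: "The next day, each patient will receive the alternate injection, and the same blood sampling protocol as the day before".
- **Section 4.1 (Patients)** defines three windows: ICU days 3 to 6, 7 to 16 and 17 to 28. It then provides for repeat testing of anyone enrolled earlier who remains in ICU and eligible when a later window opens: "the patient will be studied again according to the same study protocol". Repeat results are kept out of the primary study and analysed separately.
- **Section 7 (Statistics)** lists, as its second analysis, within-patient changes in delta AUC among patients with more than one CRH test, using mixed models or repeated measures ANOVA.

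**The concern.** The limit in section 8 equals the volume of one complete crossover test, with nothing left over. Section 4.1 nevertheless requires the full test to be repeated in eligible patients who reach a later window. No section exempts these patients from the limit or gives them a smaller sampling scheme.

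Two things are at stake. First, the ethics section states a total that is too low for any patient who completes a second test. Second, staff applying the limit literally would have to decline every repeat test, and the longitudinal analysis in section 7 would then have no data. Staff following section 4.1 would exceed the limit each time a repeat test was completed.

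**Working it through.** **Inputs** (all from the protocol)

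- Samples per session: 2 before injection (−15 and 0 min) and 8 after (5, 10, 15, 30, 45, 60, 90, 120 min) (section 5.1)
- Volume per sample: 4 ml (section 5.1)
- Sessions per crossover test: 2, on consecutive mornings (section 5.1)
- Tests per patient: 1, 2 or 3, because the three cohort windows do not overlap and section 4.1 repeats the test at each later window if the patient is still eligible
- Stated limit: 80 ml per patient (section 8)

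**Reproducing the protocol's own figures**

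- Per session: (2 + 8) × 4 ml = 40 ml, which agrees with section 5.1.
- Per crossover test: 2 × 40 ml = 80 ml, which agrees with section 8 for a patient tested once.

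**Extending to repeat tests**

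Cumulative volume = 80 ml × number of tests.

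| Tests in one patient | Cumulative volume | Ratio to the 80 ml limit |
|---|---|---|
| 1 | 80 ml | 80 / 80 = 1 |
| 2 | 160 ml | 160 / 80 = 2 |
| 3 | 240 ml | 240 / 80 = 3 |

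**Check against the daily figure**

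Each session takes 40 ml. Every session is held at the same hours of the morning, so no patient can have two on one day. The 40 ml per day quoted in sections 5.1 and 8 is therefore met however many tests a patient has. The conflict is only with the per-patient total.

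**The case against.** The best defence is that 80 ml was meant per two-day test. The figure is exactly one test. The parenthesis beside it refers to a daily volume. Section 4.3(a) also describes the monitoring time per patient as 4.5 hours over two mornings, which is again one test, although re-testing had already been introduced in section 4.1. This is probably what the authors intended, and on that reading only a qualifier is missing. But the sentence in section 8 speaks of a total and attaches it to the patient. Section 4.3(a) at least ties its hours to patients of each cohort and two consecutive mornings; section 8 has no such tie. Someone reading section 8 alone would take 80 ml as the most that any patient will give.

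Other parts of the defence stand in full. The component sums are correct, so this is an inconsistency of scope between sections and not a miscalculation. The only benchmark the protocol cites, 40 ml per day, is kept. Repeat tests feed only the separate longitudinal analysis.

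A reader might also infer more than the documents support:

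- **That the patients who stay longest are the ones affected.** The excess depends on having been enrolled in an earlier cohort. A patient first enrolled in the day 17 to 28 window gives 80 ml, while one tested in the first two windows gives 160 ml and may have had a shorter stay.
- **That consent was given on a wrong figure.** The consent forms are not available here, and they may already describe the cumulative volume.
- **That the true excess is larger because of blood discarded when sampling from catheters.** The protocol gives no discard volume, and the figures above do not depend on one.

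**Conclusion.** The point holds as a contradiction between sections. A total of 80 ml per patient and a full repeat of the test in later windows cannot both be followed. The cumulative volume is 160 ml after two tests and 240 ml after three. The result rests on two assumptions, both taken from the text: that a repeat test uses the complete sampling scheme of section 5.1, and that the section 8 limit means what it says, a total per patient.

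The reach is limited. Only patients tested in more than one window are affected, and the protocol does not say how many to expect. The primary comparison of the cohorts with the healthy controls, the sample size and the power do not change. Nor do the documents show the planned within-patient analysis to be lost: that follows only if the limit is enforced literally, which is the less likely intention. The point should still be corrected, because it concerns a stated limit in the ethics section, leaves staff with two incompatible instructions, and is cheap to put right.

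**What to change.** Reconcile sections 4.1, 5.1 and 8 by stating whether 80 ml applies to each two-day test or to the patient over the whole study.

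- **If per test:** reword the limit in section 8 accordingly, give the cumulative volume for patients tested twice (160 ml) or three times (240 ml) under the present scheme, and check that the consent forms agree.
- **If per patient:** state that the re-testing in section 4.1 and the second analysis in section 7 cannot be done as written, and amend both.

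Which limit is appropriate is for the investigators and the ethics committee; this review does not propose one. On the first reading the cost is a sentence or two in section 8, a cross-reference from section 4.1, and a change to the consent forms only if they turn out to disagree. On the second, the repeat tests and the longitudinal analysis would have to be withdrawn or redesigned. Neither option touches the primary analysis or the sample size.
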